7.2 Analysis methods

The primary analysis will be based on the Intention-to-Treat population. A linear mixed effects model for the GAD-7 at 12-week will be used for the primary effectiveness analysis. The model will include random intercepts for site and therapist with the therapist factor nested within sites. The analysis will define the site variable using the 20 NHS research sites that provided therapists. UEA, which functioned solely as a PIC site for self-referred participants, will not be included in this variable. Participants who initially signed up through UEA were reallocated to one of the 20 NHS sites (these allocations are recorded in REDCap under the site_allocation variable in the Site Allocation form). The model will be estimated via maximum likelihood method and the contributions of the random effects will be assessed via likelihood ratio test. Any of the random effects not having statistically significant contribution to the improvement of the model fit will be removed from the final analysis model. The estimated variance component(s) of the random effects remained (if any) in the final analysis model will be reported along with 95% confidence interval(s). If neither of the random effects contributes significantly to the model fit, the analysis model will be reduced to a standard multiple linear regression model. The model will include

the treatment group indicator as a fixed factor and will also account for the baseline outcome (GDA-7) and ethnicity (Asian, Black, White, Mixed or Other ethnic groups) as adjusting variables. If the residuals from the model do not follow a normal distribution, appropriate transformations of the outcome data will be considered, e.g., a logarithmic transformation in the case of a positively skewed distribution. The distribution of the residuals will be assessed visually and pertinent summary statistics (e.g., the skewness statistic) will be checked. Statistical significance will be set at 5% (two-sided). Parameter estimates will be presented with 95% confidence intervals.

The analyses of secondary outcomes such as PHQ-9, CompACT, and EACQ will follow an analogous approach. In each case, an appropriate linear mixed effects or linear regression model with inclusion of the random effects, outcome at baseline (if available), any potential confounding variables (e.g., participant characteristics showing significant imbalance at baseline between the trial arms), treatment group and minimisation factors (GAD-7 severity range of mild, moderate, severe and ethnicity groups of Asian, Black, White, Mixed or Other ethnic groups) will be constructed. The assumptions of the models, most notably the distribution of the residuals, will be assessed visually and with reference to pertinent statistics (e.g. the skewness statistic).

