6.1.1 Study Setting

Potential participants will be identified through primary and secondary care services, including GP practices, Community Mental Health Teams and memory clinics. In addition, various methods (used successfully in our feasibility study) will be used in the community to reach potential participants. This includes advertisement through local newspapers (the most successful strategy in our feasibility study), Join Dementia Research and local community services, including dementia cafés.

Culturally acceptable recruitment strategies recommended by our PPI members will also be used to maximise recruitment of participants from ethnic minority groups. These include visiting places of worship, contacting local faith leaders and circulating the information through social media and WhatsApp befriending groups, which have become popular during the COVID-19 pandemic. Setting up these approaches will be supported by our collaborating partner, the Centre for Ethnic Health Research.

Ten NHS Participant Identification Centres (PICs), which are mainly likely to be GP practices, will be set up for only identifying potential participants. No further research activity will take place at PICs. In addition to 10 PICs, a maximum of 20 trial sites (36 therapists) will be identified and the requirements for these trial sites are described below.

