6.4.2.2 Treatment Schedule

Participants will continue to receive any routine support over 12 weeks. They will receive no contact with trial therapists as described in ARM A.

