6.7 Sample Size

Participants in our feasibility study had an average reduction of 26% on GAD7. A reduction of 20% on GAD7 is considered to be a Minimum Clinically Important Difference[23]. Using a conservative reduction of 20% from the mean baseline GAD7 score, and using the variability estimated from our feasibility study, a clinically-meaningful effect size is estimated to be d = 0.55 for our sample. Recent systematic reviews of RCTs of self-help ACT and mindfulness-based interventions (mainly for individuals with a mental or physical health condition) demonstrated a pooled effect size of d = 0.35 for anxiety[42, 43]. One of these reviews, which solely focused on RCTs of self-help ACT[42] demonstrated that when analysis was limited to studies that utilised guided self-help ACT, the pooled effect size increased to d = 0.61, while limiting analysis to studies that used an unguided approach decreased the pooled effect size to d = 0.16. The effect size calculated from our feasibility study of iACT4CARERS, which utilised a guided approach, is in line with the effect size reported in previous reviews.

To ensure adequate statistical power, we have decided to take the most conservative approach possible and have used an effect size of d = 0.35 in our sample size calculation. To detect the effect size of d = 0.35 between the two trial arms at a two-tailed significant level of 5% with 90% statistical power, each arm requires 173 participants (i.e. 346 in total). Twenty seven percent of carers were lost to follow-up in our feasibility study. Assuming a dropout rate of 30%, a total of 496 carers will be recruited over 20 months (i.e. 24.8 participants per month).

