6.9.1.3 Allocation Implementation

The unblinded Trial Manager based at NCTU will be informed of the allocation. The Trial Manager will set up the account for the online intervention for participants randomised to iACT4CARERS plus TAU and will send an email containing a link to the iACT4CARERS website and unique login details to them. Participants recruited at trial sites will be assigned to the trial therapist from the same site. Participants recruited from other resources (e.g. self-referral from the community) will be randomly assigned to one of the trial therapists across trial sites. The allocated trial therapist will also receive a notification from the unblinded Trial Manager via email. Research Associates (outcome assessors) will not have access to the allocation at any time during the study.

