4.3 Sample size

Participants in our feasibility study had an average reduction of 26% on GAD-7. A reduction of 20% on GAD-7 is considered to be a Minimum Clinically Important Difference [13]. Using a conservative reduction of 20% from the mean baseline GAD-7 score, and using the variability estimated from our feasibility study, a clinically-meaningful effect size is estimated to be d = 0.55 for our sample. Recent systematic reviews of RCTs of self-help ACT and mindfulness-based interventions (mainly for individuals with a mental or physical health condition) demonstrated a pooled effect size of d = 0.35 for anxiety [14, 15]. One of these reviews, which solely focused on RCTs of self-help ACT [14] demonstrated that when analysis was limited to studies that utilised guided self-help ACT, the pooled effect size increased to d = 0.61, while limiting analysis to studies that used an unguided approach decreased the pooled effect size to d = 0.16. The effect size calculated from our feasibility study of iACT4CARERS, which utilised a guided approach, is in line with the effect size reported in previous reviews.

To ensure adequate statistical power, we have decided to take the most conservative approach possible and have used an effect size of d = 0.35 in our sample size calculation. To detect the effect size of d = 0.35between the two trial arms at a two-tailed significant level of 5% with 90% statistical power, each arm requires 173 participants (i.e. 346 in total). Twenty seven percent of carers were lost to follow-up in our feasibility study. Assuming a dropout rate of 30%, a total of 496 carers will be recruited over 20 months (i.e. 24.8 participants per month).

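### The primary model's therapist random effect is undefined for the TAU arm; the SAP should restrict it to the iACT4CARERS arm and keep it regardless of the likelihood ratio test

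*SAP*

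**What the plan says.** The primary analysis in SAP 7.2 is a single linear mixed model for 12-week GAD-7 on all randomised participants. On its random part the SAP says: "The model will include random intercepts for site and therapist with the therapist factor nested within sites". Protocol 6.10.4.1 also gives random intercepts for site and therapist. SAP 7.2 then tests each random effect by likelihood ratio and removes any that is not significant, falling back to ordinary multiple regression if neither is. The secondary outcomes take an analogous approach.

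Of the control arm, Protocol 6.4.2.2 says: "They will receive no contact with trial therapists as described in ARM A". Protocol 6.9.1.3 describes therapist assignment while explaining how access to the intervention is set up. For carers not recruited at a trial site it says: "Participants recruited from other resources (e.g. self-referral from the community) will be randomly assigned to one of the trial therapists across trial sites". That sentence does not name an arm, but the text around it concerns the intervention arm.

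Site is handled explicitly. SAP 7.2 says: "Participants who initially signed up through UEA were reallocated to one of the 20 NHS sites", without limiting this to one arm, and names the REDCap variable that holds the allocation. There is no equivalent statement for therapist.

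**The concern.** Clustering by therapist exists in one arm only. A random intercept for therapist, written without restriction in a two-arm model, needs a therapist value on every record, and TAU carers have none. The analyst must then add something that the SAP does not contain. If the field is blank, standard software discards those records and the treatment effect cannot be estimated. If it is filled in, the model assigns a therapist variance component to carers who saw no therapist, and the result depends to some degree on the code chosen. This is the model behind the trial's main confidence interval and p-value, so the choice should not be made after the data are in hand.

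**Working it through.** **Inputs.** Protocol 6.1.1: "a maximum of 20 trial sites (36 therapists) will be identified". SAP 4.3: "at a two-tailed significant level of 5% with 90% statistical power, each arm requires 173 participants", and the authors "have used an effect size of d = 0.35 in our sample size calculation". The documents give no therapist ICC (ρ), so ρ = 0 to 0.10 is assumed.

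**1. The plan's own figure.** With SD = 1, n per arm = 2(1.96 + 1.2816)²/0.35² = 171.5, or 172 by the normal approximation; the t-test solution is 172.5, so 173. The SE is √(2/173) = 0.1075 and power is Φ(0.35/0.1075 − 1.96) = 90.2%. Dropout: 173/0.70 = 247.1, so 248 per arm and 496 in total. The figure reproduces, with no allowance for clustering.

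**2. The partially nested design.** Analysed participants per therapist: 173/36 = 4.8. Var(intervention mean) = [1 + (173/36 − 1)ρ]/173 and Var(TAU mean) = 1/173.

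- ρ = 0.05: √[(1.190 + 1)/173] = 0.1125; power 87.5%.
- ρ = 0.10: √[(1.381 + 1)/173] = 0.1173; power 84.7%.

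Both are before any gain from the planned baseline adjustment.

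**3. What the TAU code does to the fitted SE.** Simulated trials: 346 analysed, 36 therapists in 20 sites, site ICC 0.01, maximum likelihood, no covariates, 500 trials per scenario. Mean model SE before any term is removed:

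| Treatment of TAU | ρ = 0.05 | ρ = 0.10 |
|---|---|---|
| Therapist effect in intervention arm only | 0.1113 | 0.1153 |
| Each TAU carer a separate level | 0.1119 (+0.5%) | 0.1164 (+1.0%) |
| One TAU pseudo-therapist per site | 0.1123 (+0.9%) | 0.1169 (+1.4%) |
| One TAU cluster across all sites | 0.1413 (+27%) | 0.1981 (+72%) |

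A second set of 1,500 trials per scenario gave mean SEs of 0.112 to 0.114 (ρ = 0.05) and 0.117 to 0.119 (ρ = 0.10) for the first three rows, with power within about 1 point. The shared cluster inflated the SE by about 33% and 87%. The two sets differ in settings and carry simulation error, but agree on the pattern.

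**4. The removal rule.** In the larger set, the likelihood ratio test (5%, one degree of freedom) removed a correctly specified therapist term in about 88% of trials at ρ = 0.05 and 66% at ρ = 0.10. In the smaller set it was kept in 8% and 26%, so removed in 92% and 74%. When the term is removed, the model reports about 0.1075 where the design SE is 0.1125 or 0.1173:

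- ρ = 0.05: 0.1075/0.1125 = 0.956, so 4.4% too small; two-sided error 2[1 − Φ(1.96 × 0.956)] = 6.1%.
- ρ = 0.10: 0.1075/0.1173 = 0.917, so 8.3% too small; two-sided error 2[1 − Φ(1.96 × 0.917)] = 7.2%.

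**5. The price of keeping the term.** At ρ = 0 the mean SE was 0.1089 with the intervention-only term kept, against 0.1069 for ordinary regression: 0.1089/0.1069 = 1.019, about 2% wider.

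**The case against.** The case against is strong on size. Four larger readings are tempting, and the documents do not support them.

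- **That the model cannot be fitted.** A therapist effect entered through the arm indicator keeps both arms, runs in the planned software, and is not excluded by the SAP. Nor does the SAP say in terms that every participant has a therapist intercept; that is inferred from one unrestricted model. Loss of the TAU arm through blank codes would be noticed at once, because no treatment effect could be estimated.
- **That the coding decides the standard error, with a severe loss of power.** The large inflation needs one TAU cluster spanning all sites, which contradicts the nesting in the quoted sentence. Under nested syntax, a single TAU code becomes one level per site. A closed-form calculation that gives TAU pseudo-therapists the full therapist variance also overstates the effect, because the fitted model estimates one pooled component from both arms. The removal rule then takes the term out in most trials anyway.
- **That the site label of self-referred TAU carers should be dropped.** SAP 7.2 defines site for these carers. No material harm has been shown, and dropping the label would leave a second factor undefined.
- **That the sample size is inadequate.** At an assumed ICC of 0.05, power is 87.5% before baseline adjustment, which should recover some of the loss.

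What remains is that the SAP states a therapist term with no meaning in one arm and does not say how to resolve it. That a sensible analyst would probably choose well is not pre-specification.

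**Conclusion.** The point holds as a specification gap in the primary model with a small expected numerical effect. The therapist factor is undefined for TAU, and the partially nested form is the one that matches the design. Among codings that respect nesting within site, the choice moves the SE by about 1% to 2% on average. Only a code outside the stated nesting does serious damage: about 27% to 33% at ICC 0.05 and 72% to 87% at ICC 0.10, before the removal step. The removal rule matters at least as much as the choice among nested codings, since it usually discards the term and leaves an SE about 4% to 8% below the design value in those trials.

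These sizes rest on assumed therapist ICCs of 0.05 to 0.10, 173 analysed per arm, 36 therapists and no covariates. If Protocol 6.9.1.3 was meant to give TAU carers a nominal therapist label, neither document says so, and such a label would still describe no contact.

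**What to change.** In SAP 7.2:

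1. State that the therapist random effect applies to the intervention arm only: a random coefficient on the arm indicator by therapist within site, zero for TAU, with no separate therapist intercept.
2. State what TAU records carry in the therapist field. It must be non-missing so that the records are retained; with a zero coefficient, the value itself has no influence.
3. Exempt this term from the likelihood ratio removal rule.
4. Apply the same structure to the secondary outcomes, and check the reference to random effects in the serious adverse event model of SAP 7.6.

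Leave the site definition as it is. REML, Kenward-Roger degrees of freedom and arm-specific residual variances are optional refinements.

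The cost is SAP wording and a different random-effects statement in the same software, with no new data. The downside is a slightly wider interval. SAP section 5 plans analysis blind to group identity, and a therapist field filled for one arm reveals that arm. The coding should therefore be fixed before the analyst receives the data.

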6.8 Recruitment and Retention

6.8.1 Recruitment

In our feasibility study, 76% of participants who received iACT4CARERS had self-referred from the community, and 24% of participants were referred from NHS services[22]. Therefore, multiple recruitment strategies will be used to reach out to potential participants, and both clinician and self-referrals will be accepted.

- Recruitment through NHS PICs: PICs are most likely to be primary carer services (GPs). PICs will search their database to identify potentially eligible participants. An invitation letter, including PIS, an expression of interest card and a pre-paid return envelope, will be sent to potential participants from PICs. If interested, participants will be asked to return the expression of interest card, providing their preferred contact detail, to the study team at UEA using the return envelope. Carer-focused publicity materials (study flyer and video-recorded study advertisement) will also be made available in waiting areas of the services and on their social media platforms (e.g. twitter, Facebook, website) to promote the study.
- Recruitment through NHS trial sites: Potential participants will be identified through trial sites. These services will include Community Mental Health Teams and memory clinics. Clinicians will approach potentially eligible participants and will seek verbal consent for Research Associates based at UEA to contact the participant with further information about the study if they express interest. A nominated individual at trial sites will share contact detail of potential participants (name, telephone number and email) with UEA via the central database (REDCap), stored on

servers based at NCTU. The central database will also ask the nominated individual to indicate that they have checked the basic eligibility criteria (being a family carer, interested in online psychological support and having access to internet) and have obtained verbal consent. Research Associates will then arrange a screening appointment. Carer-focused publicity materials (study flyer and video-recorded study advertisement) will also be made available in waiting areas of the services and on their social media platforms (e.g. twitter, Facebook, website) for those who may wish to self-refer.

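### SAP 7.2 shares one NHS-site intercept across both arms, self-referred TAU carers included, so the standard error is somewhat too small if delivery differs between sites

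*SAP*

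**What the plan says.** SAP 7.2 specifies a linear mixed model for GAD-7 at 12 weeks in the ITT population, with random intercepts for site and for therapist nested in site. The site variable consists of the 20 NHS sites that provided therapists. UEA, the sign-up point for self-referrals, is left out of it: "Participants who initially signed up through UEA were reallocated to one of the 20 NHS sites", as recorded in `site_allocation`. No arm is excepted. There is no site-by-arm term, and the therapist value for a TAU carer is not stated. A random effect that fails a likelihood ratio test is removed, and the model may end as ordinary regression.

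The Protocol describes what that label can mean. Section 6.9.1.3: "Participants recruited from other resources (e.g. self-referral from the community) will be randomly assigned to one of the trial therapists across trial sites". Section 6.4.2.2, on TAU carers: "They will receive no contact with trial therapists as described in ARM A". Section 6.1.2 gives screening, consent and assessment to UEA staff, not to the sites. In the feasibility study "76% of participants who received iACT4CARERS had self-referred from the community" (6.8.1).

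SAP 7.3.3 keeps the referral source in a separate variable, `referral_site`, and adds referral route to the primary model if the arms differ on it.

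**The concern.** For an intervention carer, the allocated site is where the therapist works. For a self-referred TAU carer it describes nothing that happened to them. A single shared intercept nevertheless assumes that a TAU carer labelled with site k moves up or down with the intervention carers treated from site k.

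Let u_k be the delivery effect of site k, with variance σ², and let w1k and w0k be the shares of each arm labelled k. If delivery affects the intervention arm only, sites add σ²·Σ w1k² to the variance of the arm difference. The shared intercept instead counts σ²·Σ (w1k − w0k)², which is small when the two arms have similar site shares. The variation is treated as if it cancelled. Because this is the primary model, the headline interval and p-value are affected.

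**Working it through.** **1. The plan's own figure.** Protocol 6.7: "have used an effect size of d = 0.35 in our sample size calculation", "at a two-tailed significant level of 5% with 90% statistical power". The normal formula gives n = 2(1.960 + 1.282)²/0.35² = 171.5, so 172 per arm; the t-test version gives 172.5, so 173. Dropout: 173/0.7 = 247.1, so 248 per arm and 496 in total, which agrees with "Assuming a dropout rate of 30%, a total of 496 carers will be recruited over 20 months". With SD 1, SE = √(2/173) = 0.1075 and power is 90.2%. The figure is reproduced. It allows nothing for site or therapist variation.

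**2. Exact SE when delivery varies in the intervention arm only.** From the documents: 173 per arm, 20 sites, 36 therapists. Assumed: 16 sites with two therapists and four with one (16×2 + 4 = 36), carers spread at random over therapists, no site effect common to both arms, and variance shares r (site) and q (therapist).

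- a = 68/1296 + (1 − 68/1296)/173 = 0.0525 + 0.0055 = 0.0579
- t = 1/36 + (35/36)/173 = 0.0334
- SE² = (1 − r − q)/173 + r·a + q·t + 1/173
- r = 0.05, q = 0: 0.00549 + 0.00290 + 0.00578 = 0.01417, SE = 0.119
- r = 0.02, q = 0: 0.00566 + 0.00116 + 0.00578 = 0.01260, SE = 0.112
- r = q = 0.025: 0.00549 + 0.00145 + 0.00083 + 0.00578 = 0.01356, SE = 0.116

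**3. SE reported by the models.** Mean model SE from 800 simulated trials per scenario, fitted by maximum likelihood, divided by the exact SE. Implied type I error, 2[1 − Φ(1.96 × ratio)], is in brackets. The removal test used a boundary-corrected 5% level.

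| Site / therapist share | Site only, or therapist also given to TAU | Site shared, therapist in intervention arm only | SAP removal rule, across codings | Site + site-by-arm + therapist in intervention arm, none removed |
|---|---|---|---|---|
| 2% / 0 | 0.95 (6.2%) | 0.98 (5.6%) | 0.95-0.96 (5.9-6.2%) | 1.00 (5.1%) |
| 2.5% / 2.5% | 0.92 (7.1-7.2%) | 0.96 (5.9%) | 0.92-0.95 (6.4-7.1%) | 0.99 (5.2%) |
| 5% / 0 | 0.90 (7.8%) | 0.94 (6.6%) | 0.90-0.92 (7.1-7.8%) | 0.98 (5.5%) |

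At zero variance the model SEs were 0.107 to 0.110 against 0.1075, so there is no shortfall. The exact SE is the yardstick because a rejection rate near 6% from 800 trials has Monte Carlo error √(0.06×0.94/800) = 0.8 points.

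**4. Further simulations at 5% site variance.** Three other null simulations gave, for the shared site term with therapist in the intervention arm only, SE ratios of 0.949 (3,000 trials), 0.931 (1,500 trials) and 0.98, with type I error of 6.2%, 6.2% and 6.1%. Limiting the site term to the intervention arm gave 0.996 (5.2%) in the first and 1.03 (5.2%) in the third. Dropping site and keeping therapist gave 0.940 (6.1%) in the second and 0.99 (5.9%) in the third.

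**5. The removal rule.** With it applied, 83% of fits fell back to plain regression in the 1,500-trial run (uncorrected cut-off) and about 72-76% in the third simulation. In the latter, type I error was 6.5% with the shared term and 6.0% even with the intervention-only term.

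**The case against.** The strongest reply is that the site label is not the main cause. At 5% site variance most fits fall back to plain regression, whose SE ratio in the 1,500-trial run was 0.898, about the same as for a shared site intercept alone (0.893). The shared term seldom reaches the final model, and relabelling TAU carers without dropping the removal rule would not cure the shortfall. This stands, and the fix therefore has to cover both.

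Second, site variance may be small: the programme is one standardised website, with common training and supervision (Protocol 6.4.1.1 and 6.3.1.4). At 1% site variance the 1,500-trial run gave 5.7% against 5.5%, within simulation noise. This also stands, and is why the size can only be given conditionally. The plan itself nevertheless models site and therapist and promises to report any variance components it retains.

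Third, carers referred by an NHS site have a real link to it in either arm, which setting the site term to zero for all TAU carers discards. That is fair, and is a reason to offer a version that keeps the shared term and adds a site-by-arm effect.

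A reader might also infer that the SAP overwrites the recruitment source. It does not: `referral_site` is kept and SAP 7.3.3 uses it. Or that TAU carers have a blank site and drop out of the analysis. Nothing in the documents says that the allocation form was completed for one arm only.

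**Conclusion.** The point holds in conditional form and deserves a change to the SAP before analysis. As worded, SAP 7.2 groups self-referred TAU carers by a site with no role in their care, and neither the shared intercept nor the removal rule carries intervention-only delivery variation fully into the standard error. That TAU carers are included is inferred from the unrestricted wording and the ITT population; the SAP does not say so arm by arm.

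The SE shortfall is nil at zero site variance, roughly 2-5% at 2%, and roughly 2-10% at 5%, where type I error is about 6-8%. The variance shares are assumptions, and the therapist coding for TAU decides where in each range the result falls.

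Three stronger readings are not supported. That the SE is too small as a matter of fact: no intraclass correlation is given. That the treatment estimate is biased: the issue shown is its precision. That a known majority of TAU carers is mislabelled: 0.76 × 173 gives about 131, but the 76% comes from a feasibility study of 33 carers at three sites and only illustrates the possible scale.

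**What to change.** In SAP 7.2:

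- State the site and therapist coding for TAU carers. Either apply both random intercepts to the intervention arm only (zero for TAU), or keep the shared site intercept and add a site-by-arm random effect in the intervention arm, with therapist in that arm only.
- Keep these terms whatever the likelihood ratio test shows.
- Do not use `site_allocation` to group self-referred TAU carers.

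Dropping the site term and keeping only therapist is not enough: it corrects the shortfall only in part. Making referral route an unconditional covariate is optional, since SAP 7.3.3 already covers it.

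The cost is a few lines of SAP text and model code, with no new data. The interval widens slightly if sites differ in delivery. If they do not, the site-by-arm version gave an SE of 0.1103 against 0.1075, about 3% larger than needed.

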4.2 Randomisation

Following baseline assessments, participants will be randomised on a 1:1 basis between iACT4CARERS plus TAU or TAU alone. Allocation will be computer-generated by a centralised system managed by NCTU ensuring concealment prior to randomisation. The sequence will be hidden from users of the database. Once allocated, a secure email will be sent to the Trial Manager and Research Lead at NCTU who will be unblinded. Minimisation will be performed with the factors collected at baseline: GAD-7 severity range (mild, moderate, severe) and ethnicity (Asian, Black, White, Mixed or Other ethnic groups). All unblinded study procedures will be conducted by the unblinded Trial Manager, NCTU Research Lead or the authorised delegate based at NCTU. Research Associates based elsewhere at UEA collecting baseline and follow-up data will be blinded to group allocation.

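### The primary mixed model is fitted by maximum likelihood with no degrees-of-freedom method named; restricted maximum likelihood with a small-sample correction would be a cheap but minor improvement

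*SAP*

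**What the plan says.** SAP 7.2 fits a linear mixed model to GAD-7 at 12 weeks with "random intercepts for site and therapist with the therapist factor nested within sites". It adjusts for baseline GAD-7 and ethnicity. On estimation it says: "The model will be estimated via maximum likelihood method". On sites: "The analysis will define the site variable using the 20 NHS research sites that provided therapists". The therapist count appears only in Protocol 6.1.1, as a planned figure: "a maximum of 20 trial sites (36 therapists) will be identified".

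Each random effect is tested by likelihood ratio. "Any of the random effects not having statistically significant contribution to the improvement of the model fit will be removed from the final analysis model". If neither survives, "the analysis model will be reduced to a standard multiple linear regression model". Variance components that remain are reported with 95% intervals. The PHQ-9, CompACT and EACQ models follow the same approach with more covariates.

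Neither document names restricted maximum likelihood (REML), a degrees-of-freedom method or a reference distribution for the treatment test. SAP section 9 names SAS 9.4 and Stata 17 but no procedure or option. No intraclass correlation (ICC) is given, and the SAP does not say how treatment-as-usual (TAU) carers enter the therapist factor.

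**The concern.** Maximum likelihood makes no allowance for the fixed effects it estimates, so its residual variance uses too large a divisor. Referring the estimate to a normal distribution also ignores the uncertainty in the variance components. Information on therapist variation is thin: 36 planned therapists with about five evaluable carers each, all in the intervention arm, since of TAU participants Protocol 6.4.2.2 says: "They will receive no contact with trial therapists as described in ARM A". The primary and secondary p-values and intervals could therefore be slightly optimistic.

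There is also an imbalance within the plan. The fallback regression would ordinarily use the unbiased residual divisor and t quantiles, so the more complex branch may receive the less careful inference.

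**Working it through.** **The plan's own figure.** For d = 0.35, two-sided 5% and 90% power, the normal formula gives 2 × (1.960 + 1.282)² / 0.35² = 171.6, so 172 per arm. The t-test version gives 172.5, so 173, as stated. With 30% dropout, 173 / 0.7 = 247.1, so 248 per arm and 496 in total, as stated.

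**Inputs.** From the documents: 346 analysed carers, 20 sites, 36 therapists. This gives 173 / 36 = 4.8 intervention carers per therapist. There are 6 fixed-effect parameters: intercept, treatment, baseline GAD-7, and three for ethnicity taken as four groups. Assumed: the ICCs (site 0 to 0.05, therapist 0 to 0.20), equal-probability assignment to therapists, and normal quantiles with maximum likelihood.

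**Site only kept.** Treatment is compared within site, so the number of sites barely enters. Two factors remain:
- Divisor: √(340/346) = 0.991.
- Quantile: 1.960 / 1.967 (t on 340 df) = 0.996.

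The product is 0.988, that is 1.2% narrower. Simulation also gave 0.988.

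**Therapist kept.** Compared with REML and Satterthwaite degrees of freedom for the same model, simulated width ratios were 0.967 to 0.969 (about 3% narrower). They were about 0.945 (5.5% narrower) when TAU carers formed one extra cluster per site. In separate runs that kept both effects, median Satterthwaite degrees of freedom were 42 to 53. There the quantile ratio alone is 1.960 / 2.018 = 0.971 to 1.960 / 2.006 = 0.977, which accounts for most of the 3%.

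**Both effects always kept** (3,000 runs per setting, therapist coded in the intervention arm only). Coverage was 93.8 to 95.3% for maximum likelihood with z and 94.6 to 95.8% for REML-Satterthwaite, with Monte Carlo standard error about 0.4 points.

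**Under the SAP's keep-or-drop rule** (3,000 runs per row, no site variance, maximum likelihood with z; standard error of retained coverage = √(0.95 × 0.05 / runs)):

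| Therapist ICC | Runs keeping therapist alone | Coverage in those runs (SE) | Coverage when both were dropped |
|---|---|---|---|
| 0.02 | 98 | 95.9% (2.2) | 94.3% |
| 0.05 | 290 | 94.5% (1.3) | 93.7% |
| 0.10 | 1,020 | 95.9% (0.7) | 91.4% |
| 0.20 | 2,451 | 94.7% (0.4) | 88.2% |

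With TAU carers as extra clusters, coverage with therapist kept was 96 to 98%. With a true site ICC of 0.05 and no therapist effect, coverage when site alone was kept was 94.0%. With both ICCs at 0.05, runs that kept any effect covered 93.4%, against 93.8% for REML-Satterthwaite. That shortfall came from the 1,150 runs that kept site alone (92.2%), where the therapist effect had been deleted, and REML hardly changes it.

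**Overall type I error under the same rule** (separate simulation, 2,000 null runs per row, standard error about 0.5 points):

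| Site / therapist ICC | ML, z | REML, Satterthwaite | Difference (points) |
|---|---|---|---|
| 0.05 / 0.05 | 5.75% | 5.55% | 0.20 |
| 0 / 0.10 | 6.5% | 6.3% | 0.20 |
| 0 / 0.20 | 6.7% | 6.25% | 0.45 |

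In this simulation, maximum likelihood type I error given retention was 4.7%, 4.3% and 6.2%, on both sides of 5%. In the first setting the earlier simulation gave 100 − 93.4 = 6.6%, so the two agree only loosely there.

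**Retained variance components.** Mean maximum likelihood estimates of the therapist component over two sets of runs were 0.125 and 0.150 for a true 0.05, 0.145 and 0.149 for 0.10, and 0.201 and 0.207 for 0.20. For site they were 0.065 for 0.05 and 0.101 for 0.10.

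**The case against.** The strongest case against is that this is only an unspecified option with a negligible effect. Several parts of it stand.

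- A reader might infer that every retained interval is too narrow. The SAP's own rule contradicts this. An effect stays only when the likelihood ratio test is significant, which selects samples with a high variance estimate, and coverage with therapist retained was then close to nominal.
- A reader might infer that the reported variance components will be biased low. Only retained components are reported, and for the same reason they come out at or above the truth. REML would not correct that.
- A reader might blame the small number of sites. SAP 4.2 says "participants will be randomised on a 1:1 basis between iACT4CARERS plus TAU or TAU alone", so treatment is compared within site. Only the therapist part depends on a small cluster count.
- The absence of a correction is inferred from silence, because the reference distribution is simply not stated.
- The gain is near simulation noise. With correctly coded clustering and 3,000 null runs, maximum likelihood with z gave type I error of 5.2%, 5.6% and 5.8%, against 4.7%, 5.1% and 4.7% for REML-Satterthwaite, with standard error about 0.4 points. Ratios of standard errors were 0.989 to 0.996 for maximum likelihood and 1.007 to 1.011 for REML, so the two miss by similar amounts in opposite directions.

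What does not stand is the conclusion that nothing need change. The estimator is fixed in the text, the reference distribution for the primary p-value is open, and the uncorrected interval was narrower than the corrected one in every setting examined. If the sponsor also stops deleting random effects, every primary analysis becomes one with random effects kept, and the choice then applies each time.

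**Conclusion.** The point holds as a minor improvement. With normal quantiles, the treatment interval is about 1% (site only) to 3% (therapist kept) narrower than the corrected one, and about 5.5% under the extra-cluster coding of TAU carers. Overall type I error under the SAP's rule changes by about 0.2 to 0.5 points at assumed therapist ICCs of 0.05 to 0.20.

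These sizes rest on assumed ICCs, on the planned count of 36 therapists and on normal-based inference, none of which the SAP settles. The documents do not support a claim that the primary result would be seriously anti-conservative because of the estimator. The larger loss comes from removing random effects by significance test: the therapist effect was kept in only about 10% of runs at ICC 0.05 and 34% at 0.10, and coverage after both effects were dropped fell as low as 88.2% at ICC 0.20.

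**What to change.** In SAP 7.2, and in the secondary-outcome models that follow it, replace maximum likelihood with restricted maximum likelihood with Kenward-Roger or Satterthwaite degrees of freedom, and name which one. Both are available in the named software. The likelihood ratio comparison of random effects stays valid because the models compared have identical fixed effects.

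The cost is one model option and slightly wider intervals: 1 / 0.988 = 1.012 (site only), 1 / 0.968 = 1.033 (therapist kept) and 1 / 0.945 = 1.058 (TAU as extra clusters). Design, data collection and sample size are unaffected.

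This edit is best made together with a decision on the significance-based removal of random effects and a statement of how TAU carers are coded in the therapist factor. It repairs neither of those.
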